6.3.3.5 Dose Modifications for Other Non-Hematologic Toxicity

CTC Grade	Action	5-FU, % of	Oxaliplatin, % of		
		Previous Dose	Previous Dose		
1	Continue therapy	100	100		
2	Continue therapy	100	100		
3	Resume when	75 ^{1, 3}	75 ^{2, 3}		
	toxicity <= Grade 1				
4	Resume when	50 ^{1, 3}	50 ^{2, 3}		
	toxicity <= Grade 1				

¹See section 6.4.4 for dose reductions of 5-FU for Hand-Foot-Skin Reaction.
 ²No Dose reduction of Oxaliplatin for Grade 3 or 4 Hand-Foot-Skin Reaction.
 ³No dose reduction of 5-FU or Oxaliplatin need to be made for asymptomatic Grade 3 or 4 Amylase or Lipase elevation.

Pertains to treatment-related toxicity, not including diarrhea, nausea/vomiting, melena/hematemesis, neurologic toxicity (see above). Sorafenib dose should be adjusted as per the table in Section 6.4.1. For hematologic toxicity, see Section 6.3.2.

Doses of chemotherapy that have been reduced will not be re-escalated. Patients who do not recover to Grade 1 within 6 weeks will go off study.

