3.0 STUDY POPULATION

- 3.1 Inclusion Criteria
 - Histologically confirmed advanced HCC
 - No cirrhosis or Child-Pugh A (CTP score < 7) cirrhosis (See Appendix A)
 - Barcelona Clinic Liver Cancer (BCLC) stage C, and those with BCLC-B Stage who cannot tolerate or failed TACE (See Appendix B)
 - Patients must have measurable lesions
 - All patients must have adequate hepatic function: total bilirubin ≤ 2.0 mg/dl; AST and ALT ≤ 6x upper limits of normal.
 - Adequate renal function: Serum creatinine ≤ 2.0 mg/dl.
 - Adequate bone marrow function defined as:
 - Absolute neutrophil count \geq 1,500/mm3
 - Platelets \geq 100,000mm3
 - Hemoglobin \ge 10 g/dl
 - No prior systemic regimens for HCC
 - Patients with a prior history of liver directed therapy for their HCC (chemoembolization, radioembolization, bland embolization, radiation therapy, radiofrequency ablation, microwave ablation) can participate in the study if the liver-directed therapy was performed more than 4 weeks prior to their first dose of sorafenib and measurable lesions present outside of previously treated field
 - Chronological age \geq 18 years.

- ECOG performance status ≤ 1
- Life expectancy \geq 12 weeks
- All acute toxic effects of any prior treatment have resolved to NCI-CTCAE v4.0 Grade 1 or less at the time of signing the Informed Consent Form (ICF).
- Subject must be able to swallow and retain oral medication.
- All patients must sign informed consent.

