6.0 DOSE MODIFICATION / TOXICITY MANAGEMENT

Study drug treatment will be modified in the event of certain adverse events, as shown in the tables below.

- Regardless of the reason for holding study drug treatment, the maximum allowable length of treatment interruption of FOLFOX is 6 weeks (the holding of 3 consecutive doses) and of Sorafenib is 3 weeks. If the patient needs to stop FOLFOX due to toxicity, they can stay on study as long as they continue with Sorafenib. If the patient needs to stop Sorafenib due to toxicity, they can stay on the study as long as they continue FOLFOX. If they need to stop both FOLFOX and Sorafenib for longer than the above time limits, they must be taken off the study and the Principle Investigator must be notified.
- Doses of chemotherapy that have been reduced will not be re-escalated.
- No held doses of Sorafenib or FOLFOX will be made up. If a patient misses a dose for toxicity, the patient will proceed to the next treatment day or cycle as scheduled.

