6.4.3 Dose modification for non-hematologic toxicities¹

Recommended dose modification for non-hematologic toxicity (excluding hypertension and hand foot skin reaction, diarrhea and fatigue.									
Grade	Dose Interruption	Dose Modification							
• Grade 0-2	Treat on time	No Change							
• Grade 3	Interrupt until ≤Grade 2	DECREASE one dose level							
• Grade 4	OFF protocol therapy	OFF protocol therapy							
 If no recovery after 21 day delay, treatment will be discontinued unless subject is deriving clinical benefit 									

¹For sorafenib dose reductions for diarrhea, nausea, and vomiting, see sections 6.3.4.1 and 6.3.4.2.

For HFSR, sorafenib and 5-FU should be both reduced; For diarrhea, sorafenib, 5-FU and oxaliplatin should all be reduced; For fatigue, sorafenib, 5-FU and oxaliplatin should all be reduced.

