Doses of sorafenib that have been reduced for any reason will not be re-escalated. For treatment-related non-hematologic toxicities, patients who do not recover to Grade 1 toxicity within 3 weeks will go off Sorafenib for the duration of the study, but they can continue with FOLFOX if they continue to meet treatment criteria for FOLFOX.

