11.2 Reporting of Serious Adverse Events

Each serious adverse event must be followed up until resolution or stabilization, by submission of updated reports to the designated person. An isolated laboratory abnormality that is assigned grade 4, according to CTC definition, is not reportable as an SAE; unless the investigator assesses that the event meets standard ICH criteria for an SAE. CTC grade 4 baseline laboratory abnormalities that are part of the disease profile should not be reported as an SAE, specifically when they are allowed or not excluded by the protocol inclusion/exclusion criteria.

When required, and according to local law and regulations, serious adverse events must be reported to the Ethics Committee and Regulatory Authorities.

All serious adverse events should be reported to Bayer within 24 hours. In the event of such an event, the investigator should refer to the Pharmacovigilance section of the contract for reporting procedures.

The Investigator may report serious adverse drug reactions (SADRs) using either:

An ADEERS form (Adverse Event Expedited Reporting System) available at http://ctep.cancer.gov/reporting/adeers.html

OR

A MedWatch form available at http://www.fda.gov/medwatch/

All reports shall be sent electronically to:

Electronic Mailbo	DX:
Facsimile:	
Address: Mail only:	Global Pharmacovigilance - USA Ba yer HealthCare Pharmaceuticals Inc.
Address:	
Reports for all Communications	Bayer products can also be phoned in via our Clinical s Dept:

Phone:

AND:

Dana Farber Cancer Institute IRB/ OHRS [name]

Phone:	
Fax:	

MedWatch 3500 Reporting Guidelines:

In addition to completing appropriate patient demographic and suspect medication information, the report should include the following information within the Event Description (section 5) of the MedWatch 3500 form:

- Protocol description (and number, if assigned)
- Description of event, severity, treatment, and outcome if known
- Supportive laboratory results and diagnostics

• Investigator's assessment of the relationship of the adverse event to each investigational product and suspect medication

Follow-up information:

Additional information may be added to a previously submitted report by any of the following methods:

• Adding to the original MedWatch 3500 report and submitting it as follow-up

• Adding supplemental summary information and submitting it as follow-up with the original MedWatch 3500 form

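### The recovery rules test an absolute Grade 1 although entry admits AST/ALT up to 6x ULN, and they disagree on restart and on who leaves the study

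*Combined protocol and SAP*

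**What the plan says.** The hepatic entry criterion in Section 3.1, repeated in the Schema, is "total bilirubin ≤ 2.0 mg/dl; AST and ALT ≤ 6x upper limits of normal".

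Section 6.3.3.5 covers other treatment-related non-hematologic toxicity. After a Grade 3 or 4 event, 5-FU and oxaliplatin resume at reduced dose once the toxicity is Grade 1 or less. It ends: "Patients who do not recover to Grade 1 within 6 weeks will go off study".

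Sorafenib has two rules. For a Grade 3 event, the Section 6.4.3 table says "Interrupt until ≤Grade 2". If there is no recovery after a 21-day delay, "treatment will be discontinued unless subject is deriving clinical benefit". The paragraph that closes Section 6.4, printed after the hypertension table in 6.4.5, covers treatment-related non-hematologic toxicity: "patients who do not recover to Grade 1 toxicity within 3 weeks will go off Sorafenib for the duration of the study". It gives no exception but allows FOLFOX to continue.

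The opening of Section 6.0 takes a component-by-component view: "If the patient needs to stop FOLFOX due to toxicity, they can stay on study as long as they continue with Sorafenib". It says the same in reverse for sorafenib, and removes a patient only when both components are stopped beyond their limits (6 weeks for FOLFOX, 3 weeks for sorafenib).

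**The concern.** The hematologic entry limits fit the hematologic grading. ANC 1,500, platelets 100,000 and hemoglobin 10 are no worse than Grade 1 in the Section 6.4.1 table. The liver limits have no such match. The protocol deliberately admits patients with raised transaminases, then measures recovery from a treatment-related rise against a fixed grade that some of them may not have met at entry. Such a patient can be fully back at the entry value and still count as unrecovered.

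Two things are at stake. One is exposure: treatment may be withheld because of the underlying liver disease. The other is interpretation: tolerability is a secondary objective (Section 1.2), and Section 10.2 counts the off-study date as an event in time to treatment failure. Because the rules also conflict with one another, two investigators following the protocol could handle the same patient differently.

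**Working it through.** No figure in the plan bears directly on this point, so the check sets the rules side by side and tests the entry limits against a range of assumed cut-points.

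**1. The recovery rules**

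| Place | Component | Recovery test | Time limit | Consequence | Entry value used? |
|---|---|---|---|---|---|
| 6.0, opening | Both | No grade given | FOLFOX 6 weeks, sorafenib 3 weeks | Stays on study while one component continues | No |
| 6.3.3.5 | FOLFOX | Grade 1 or less after Grade 3 or 4 | 6 weeks | Off study | No |
| 6.4.3 table | Sorafenib | Grade 2 or less after Grade 3 (Grade 4 ends protocol therapy) | 21 days | Discontinued, with a clinical-benefit exception | No |
| Close of 6.4 | Sorafenib | Grade 1 | 3 weeks | Off sorafenib, no exception; FOLFOX may continue | No |

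**2. AST/ALT.** The entry ceiling is 6x ULN. The Grade 1 ceiling is not printed, so it is varied as an assumption:

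- 2.5x ULN: entry values above 2.5x and up to 6x already exceed Grade 1.
- 3x ULN: above 3x and up to 6x.
- 5x ULN: above 5x and up to 6x.

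The overlap exists for any ceiling below 6x. Patients entering at or below the ceiling are not affected.

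**3. One patient followed through the rules.** Assume Grade 1 ends at 3x ULN and Grade 2 at 5x. A patient enters at 4x, has a treatment-related rise to 8x (taken as Grade 3) and returns to 4x, which is Grade 2.

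- Under 6.3.3.5, FOLFOX does not resume and the patient is off study at 6 weeks.
- Under the 6.4.3 table, sorafenib can restart one dose level lower.
- Under the close of 6.4, sorafenib stops for good at 3 weeks.
- Under 6.0, the patient stays on study if sorafenib restarted. If sorafenib stopped at 3 weeks and FOLFOX never resumed within its 6-week limit, both components are gone and 6.0 removes the patient too.

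On the same assumption, a patient who entered between 5x and 6x and returns there does not meet even the 6.4.3 grade test. Only the clinical-benefit exception remains.

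**4. Bilirubin.** Assume a Grade 1 ceiling of 1.5 x ULN and compare it with the entry limit of 2.0 mg/dL:

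| ULN (mg/dL) | 1.5 x ULN | Does 2.0 exceed it? |
|---|---|---|
| 1.0 | 1.50 | Yes |
| 1.1 | 1.65 | Yes |
| 1.2 | 1.80 | Yes |
| 1.3 | 1.95 | Yes |
| 1.4 | 2.10 | No |

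The break-even ULN is 2.0 / 1.5 = 1.33 mg/dL. Below it the affected band is narrow; at a ULN of 1.2 it runs from just above 1.8 to 2.0 mg/dL.

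**5. Sample size, for completeness.** Section 14.2.1 tests a median TTP of 7 against 5 months, one-sided 10%, 80% power. The one-sample exponential formula gives (1.2816 + 0.8416)² / (ln 1.4)² = 39.8, rounded up to 40, which matches the stated 40. The recovery rules do not enter this calculation.

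**The case against.** The strongest reply concerns scope. Sections 6.3.3.5 and the close of 6.4 cover treatment-related toxicity only, and Section 6.4.1 limits sorafenib changes to clinically significant toxicity related to protocol therapy. A raised entry value therefore triggers nothing. Once a patient is back at that value, the treatment-related part could be said to have resolved. That reading is reasonable, but the text tests a grade and does not say so. Where the protocol does provide for abnormal baseline laboratory values, it does so for reporting only: "CTC grade 4 baseline laboratory abnormalities that are part of the disease profile should not be reported as an SAE" (Section 11.2). The point survives as a rule that, read literally, gives a result that may not be intended.

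A second reply is that Grade 1 may be a deliberately cautious condition after a serious liver event. It may be. The documents give no reason for it, and caution would not explain why 6.4.3 and the close of 6.4 set different conditions for the same drug.

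A reader might infer more: that every recovery rule requires Grade 1, and that every such patient loses treatment. The documents do not support this. Section 6.4.3 uses Grade 2 with an exception, Section 6.0 and the close of 6.4 allow one component to continue, and enzymes can fall below their entry value.

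A reader might also attach a count. If 10% to 30% of patients entered above Grade 1, that would be 4 to 12 of 40. That range is assumed and describes a pool at risk, not patients removed. Each would also need a treatment-related Grade 3 or 4 rise. The documents give no rate for it, and raised AST/ALT or bilirubin is not among the expected events listed in Sections 6.1, 6.2 and 6.4.

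**Conclusion.** The point stands in a limited form. For AST/ALT, the entry limit and the Grade 1 recovery tests are inconsistent for a patient who enters above Grade 1, has a qualifying treatment-related event and returns to the entry value. This rests on one assumption, a CTCAE v4.0 Grade 1 ceiling below 6x ULN. For bilirubin it arises only if the ULN is below about 1.33 mg/dL, given an assumed ceiling of 1.5x ULN. Separately, and without any assumption about cut-points, the rules conflict on the sorafenib restart grade, on the exception after 3 weeks, and on whether failure to recover for FOLFOX means leaving the study.

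The number of patients affected cannot be derived from the documents. It would be wrong to infer damage to the primary analysis. TTP in Section 10.2 counts progression or death, not the off-study date, and sample size and power are unchanged. The consequences are possible loss of exposure, inconsistent handling between investigators, and off-study dates that reflect baseline liver disease. The last enters time to treatment failure, which Section 10.2 defines but Sections 1 and 14 do not list as an objective. The point merits correction but is not critical.

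**What to change.** Reconcile Sections 3.1, 6.0, 6.3.3.5, 6.4.3 and the paragraph closing 6.4 so that:

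- the FOLFOX and sorafenib rules state how recovery is judged when a laboratory value already exceeded Grade 1 at entry, in the same wording;
- Section 6.4.3 and the close of 6.4 give one sorafenib restart condition and one position on the exception after 3 weeks;
- Sections 6.0 and 6.3.3.5 agree on whether failure to recover ends FOLFOX or ends study participation.

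The clinical threshold is left to the investigators, and none is proposed here. The cost is a short amendment to Section 6. AST, ALT and bilirubin are already collected at screening and during treatment (Sections 5.2.1.2, 5.2.2 and 9.0), so no new data are needed and the sample size does not change.

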6.4 Dose Modification for Sorafenib

Expected adverse events from sorafenib: diarrhea (43%), increased lipase (41%), increased amylase (30%), nausea (23%), anorexia (16%), vomiting (16%), and constipation (15%), rash/desquamation (40%), hand-foot skin reaction (30%), alopecia (27%), pruritus (19%), and dry skin (11%), hyperthyroidism, hypertension (17%), angioedema, and congestive heart failure, hypoalbuminemia (49%), hemorrhage (15%) (i.e., gastrointestinal, respiratory tract and rarely cerebral hemorrhage), dyspnea (14%) and cough (13%), hypocalcemia (20%), and hypophosphatemia (40%).

6.4.1 Dose Reduction Levels

The starting dose of sorafenib is 400 mg twice a day. Study medication will be administered daily on a continuous basis.

Doses will be delayed or reduced for clinically significant hematologic and nonhematologic toxicities that are related to protocol therapy according to the guidelines shown in the Dose Delays/Dose Modifications table that follows. Dose modifications will follow predefined dose levels: Dose adjustments for hematologic toxicity are based on the blood counts obtained in preparation for the day of treatment.

Dose modification levels for sorafenib							
Dose	Sorafenib						
Starting Dose	400 mg twice daily						
1 st Dose Reduction Level	400 mg once daily						
2 nd Dose Reduction Level	200 mg once daily						

Recommended Dose Modification of sorafenib for Hematologic Toxicities										
Toxicity	ANC(x 10 ⁹ /L)	Hemoglobin (g/dL)	Platelets (x 10 ⁹ /L)	Sorafenib						
Grade 1	<lln-1.5< td="">< LLN – 10.0	<lln-75< td="">Treat on time No change	</lln-75<>	</lln-1.5<>	< LLN – 10.0	<lln-75< td="">Treat on time No change	</lln-75<>	Treat on time No change						
Grade 2	≥ 1.0 to < 1.5	< 10.0 - 8.0	≥ 50 to < 75	Treat on time No change						
Grade 3	≥ 0.5 to < 1.0	< 8.0 - 6.5	≥ 25 to < 50	Treat on time Reduce by one dose level						
Grade 4	< 0.5	Life-threatening consequence; urgent intervention indicated	<25	Delay sorafenib until toxicity resolves to Grade 2 or less then Reduce by two dose levels ¹						
Febrile Neutropenia				Sorafenib held until toxicity has resolved to Grade 2 or less; when sorafenib is restarted, reduce by one dose level ²						

6.4.2 Dose modification of sorafenib for hematologic toxicities

ANC - absolute neutrophil count

¹If the patient is at the first dose reduction level (Sorafenib 400mg po QD) or the second dose reduction level (Sorafenib 200mg po QD) already, Sorafenib will be discontinued, ² If the patient is at the second dose reduction level (Sorafenib 200mg po QD) already, Sorafenib will be discontinued,

• If no recovery after 21 day delay, treatment should be permanently discontinued.

6.4.3 Dose modification for non-hematologic toxicities¹

Recommended dose modification for non-hematologic toxicity (excluding hypertension and hand foot skin reaction, diarrhea and fatigue.									
Grade	Dose Interruption	Dose Modification							
• Grade 0-2	Treat on time	No Change							
• Grade 3	Interrupt until ≤Grade 2	DECREASE one dose level							
• Grade 4	OFF protocol therapy	OFF protocol therapy							
 If no recovery after 21 day delay, treatment will be discontinued unless subject is deriving clinical benefit 									

¹For sorafenib dose reductions for diarrhea, nausea, and vomiting, see sections 6.3.4.1 and 6.3.4.2.

For HFSR, sorafenib and 5-FU should be both reduced; For diarrhea, sorafenib, 5-FU and oxaliplatin should all be reduced; For fatigue, sorafenib, 5-FU and oxaliplatin should all be reduced.

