6.3.3 Non-Hematologic Toxicity

6.3.3.1 Diarrhea

Anti-diarrheal agents should be prescribed for diarrhea. If greater than or equal to Grade 3 uncontrolled diarrhea despite maximal antidiarrheal therapy, temporarily discontinue both chemotherapy and sorafenib. Resume chemotherapy when symptoms have subsided to Grade 1 toxicity or less. Resume with 5-FU and Oxaliplatin at 75% of the previous dose. Resume sorafenib at one dose reduction.

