6.3.3.3 Melena and Hematemesis

If melena or hematemesis occur during therapy, sorafenib and chemotherapy should be held for Grade 1 toxicities until they resolve. For patients who develop Grade 3 or 4 toxicities, therapy should be discontinued and the Principal Investigator notified.

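### For treatment-related melena or hematemesis, the 6.4.3 sorafenib table contradicts 6.3.3.3 at Grades 1 and 3, and Grade 2 has no event-specific rule

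*Combined protocol and SAP*

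**What the plan says.** Section 6.3.3.3 is the only section that sets a dosing rule for melena and hematemesis by name, and it names sorafenib. At the lowest grade, "sorafenib and chemotherapy should be held for Grade 1 toxicities until they resolve". At the top, "For patients who develop Grade 3 or 4 toxicities, therapy should be discontinued and the Principal Investigator notified". It does not mention Grade 2.

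Section 6.4.3 is the general sorafenib table for non-hematologic toxicity. Its stated exceptions are "excluding hypertension and hand foot skin reaction, diarrhea and fatigue", and its footnote redirects only diarrhea, nausea and vomiting. For Grades 0 to 2 it keeps sorafenib on schedule at the same dose. For Grade 3 it says "Interrupt until ≤Grade 2" and then "DECREASE one dose level". For Grade 4 it takes the patient off protocol therapy.

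Three other places bear on the point:

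- Section 6.4.1 introduces the sorafenib modifications as applying to clinically significant toxicities that are related to protocol therapy.
- Section 6.3.3.5, the 5-FU and oxaliplatin table for other non-hematologic toxicity, describes its scope as "not including diarrhea, nausea/vomiting, melena/hematemesis, neurologic toxicity (see above). Sorafenib dose should be adjusted as per the table in Section 6.4.1".
- The closing paragraph of 6.4.5 adds a limit for treatment-related non-hematologic events: "patients who do not recover to Grade 1 toxicity within 3 weeks will go off Sorafenib for the duration of the study".

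**The concern.** A clinician managing a gastrointestinal bleed can reach two different sorafenib instructions, depending on the section consulted. Section 6.3.3.3 sits under 6.3, which is titled for 5-FU and oxaliplatin. Someone looking up sorafenib would naturally turn to 6.4, and nothing there leads back to 6.3.3.3.

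Taken literally, 6.4.3 allows sorafenib to restart after a Grade 3 bleed for which 6.3.3.3 ends therapy. It also continues full-dose sorafenib through a Grade 2 bleed, although the milder Grade 1 bleed requires a hold.

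The event is foreseeable. Section 6.4 lists gastrointestinal hemorrhage among expected sorafenib events. The protocol also treats recent serious bleeding as a hazard at entry: 3.2 excludes patients with a non-pulmonary bleed of Grade 3 or higher in the 4 weeks before enrollment. Section 6.4.3 sets no minimum interval before restarting after such a bleed on study.

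**Working it through.** No sample-size, power or alpha figure is involved, so the check sets the rules side by side. The starting sorafenib dose is 400 mg twice daily, and 400 × 2 = 800 mg/day. One dose level down is 400 mg once daily (both from 6.4.1).

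| Grade | 6.3.3.3 (sorafenib) | 6.4.3 (sorafenib, starting from 800 mg/day) | Result |
|---|---|---|---|
| 1 | Hold until resolved | Continue 800 mg/day | Conflict |
| 2 | No rule | Continue 800 mg/day | Only the general table speaks |
| 3 | Discontinue, notify the Principal Investigator | Hold to Grade 2 or lower, then 400 mg/day | Conflict |
| 4 | Discontinue, notify the Principal Investigator | Off protocol therapy | Agree |

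**Scope.** Because of 6.4.1, the overlap covers only clinically significant events related to protocol therapy. Section 6.3.3.3 applies to any melena or hematemesis during therapy, whatever the cause. For a bleed attributed to something other than treatment, it has no competitor at Grades 1, 3 and 4.

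**Which rule is meant to govern.** Section 6.3.3.3 is specific to the event and names the drug. The scope note in 6.3.3.5 sends melena and hematemesis back to the earlier sections, which supports 6.3.3.3. Against that, 6.4.3 has its own list of exceptions and its own redirect, this event is in neither, and no section states an order of precedence.

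**Grade 2, sorafenib.** Preferring the specific rule does not help, because 6.3.3.3 has no Grade 2 rule. The 6.4.3 default applies and is less cautious than the Grade 1 rule. The closing paragraph of 6.4.5 stops sorafenib only if the event has not recovered to Grade 1 within 3 weeks, and it does not say when those weeks start.

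**Grade 2, FOLFOX.** Section 6.3.3.3 is silent and 6.3.3.5 excludes the event, so no non-hematologic rule applies. The blood-count rules in 6.3.2 still do.

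**Grade 3, meaning of discontinue.** Section 6.3.3.3 does not say that discontinuation is permanent. The diarrhea rule in 6.3.3.1 marks a pause explicitly ("despite maximal antidiarrheal therapy, temporarily discontinue both chemotherapy and sorafenib"), and 6.3.3.2 does the same for nausea and vomiting. The unqualified word in 6.3.3.3 therefore more likely means a full stop. Usage is not uniform, though, since 6.4.2 and 6.4.4 in places add that a stop is permanent. Section 6.0 lets a patient stop one regimen and stay on the other, so it is also unstated whether therapy means both.

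**The case against.** The strongest reply is that an event-specific rule naming the drug is normally read ahead of a general table headed as recommendations, so the conflict at Grades 1 and 3 is narrower in practice than the table above suggests. Restarting after a Grade 3 bleed would mean overlooking the one section written for the event, including its duty to notify the Principal Investigator. Section 6.5 allows treatment to stop for an unacceptable adverse event, and 12.3 provides for quarterly toxicity review.

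Most of this stands. It makes 6.3.3.3 the probable intent and lowers the likelihood of harm. It does not supply the missing precedence statement, and it does not touch Grade 2. The safeguards in 6.5 and 12.3 are discretionary or retrospective.

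The documents do not support several stronger inferences that a reader might draw:

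- That 6.3.3.5 sends melena and hematemesis to the sorafenib tables. Its pointer to 6.4.1 follows directly on the note excluding those events, so it concerns the other toxicities.
- That every bleed is affected, including one attributed to underlying Child-Pugh A cirrhosis. The scope statement in 6.4.1 rules that out.
- That a cumulative dose given through a Grade 2 bleed can be calculated. The 3-week clock has no defined start and the length of the event would have to be assumed.
- That the 15% hemorrhage figure in 6.4 shows how often this would arise. It covers several sites and gives no grade.

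**Conclusion.** The point holds for treatment-related melena and hematemesis. The sorafenib instructions in 6.3.3.3 and 6.4.3 contradict each other at two of four grades (1 and 3) and agree at one (Grade 4). At Grade 2 only the general sorafenib table applies, and FOLFOX has no non-hematologic rule. Grade 2 is the main substantive gap, because a worse bleed is handled less cautiously than a milder one. At Grades 1 and 3 the defect is a missing exclusion and cross-reference around a rule that is probably meant to prevail.

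This rests on a literal reading of the exceptions and footnote in 6.4.3, and on the absence of any precedence statement. That Grade 3-4 discontinuation is permanent remains an inference. It would also go too far to say that the protocol clearly directs a restart after a Grade 3 bleed: one section permits it, and the more specific section says otherwise. The matter is patient safety and consistent dosing, and should be corrected. Nothing here affects time to progression, power or sample size.

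**What to change.** 1. In 6.4.3, add melena and hematemesis to the listed exceptions and to the footnote, with a pointer to 6.3.3.3. In the same edit, correct the footnote's references from 6.3.4.1 and 6.3.4.2, which do not appear in the protocol, to 6.3.3.1 and 6.3.3.2.
2. In 6.3.3.3, extend the hold-until-resolved rule to Grade 2 for sorafenib and FOLFOX, so that Grade 2 is handled at least as cautiously as Grade 1. The investigators should set the restart dose.
3. In 6.3.3.3, have the investigators state whether discontinuation at Grades 3 and 4 is permanent and whether it covers both sorafenib and FOLFOX.

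The cost is a wording amendment to two sections, with IRB approval under 13.1. It requires a few clinical decisions: the Grade 2 hold, the restart dose, and the permanence and scope of discontinuation. No visits, tests or patients are added.
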